### **7.2.2. Exclusion Criteria**

A subject will be excluded from the study if the subject meets any of the following criteria:

1. History of seizure disorder; undergoing abrupt discontinuation of alcohol, benzodiazepines, barbiturates or antiepileptic drugs; or any other condition that increases the risk of seizure such as stroke, significant head injury, tumor or infection of the central nervous system, arteriovenous malformation, neuroleptic malignant syndrome/serotonin syndrome, or clinically significant, as deemed by the investigator, metabolic disorders (e.g., clinically significant hypoglycemia, hyponatremia, severe hepatic impairment, and hypoxia).
2. Is considered by the investigator, for any reason (including, but not limited to, the risks described as precautions, warnings, and contraindications in the current version of the Investigator's Brochure for AXS-05 tablets), to be an unsuitable candidate to receive AXS-05.
3. If the subject is currently receiving or plans to use drugs with known bupropion interactions (as listed in the Wellbutrin SR package insert), Principal Investigator is aware of any potential drug interaction and has deemed the subject acceptable to participate.
4. Any current or recent medical, psychiatric, or social condition that, in the investigator's opinion, is likely to interfere with the conduct of the study, confounds the interpretation of study results, or endangers the subject's well-being. This includes (but is not limited to) any clinically significant oncologic, hematologic, endocrine/metabolic, cardiovascular, respiratory, renal, hepatic, gastrointestinal, infectious or neurologic disease or has a chronic disease which is unstable or progressive.
5. History of allergy or hypersensitivity to bupropion, dextromethorphan, opiate drugs (e.g., codeine, etc.), or any other ingredient in the study medication.
6. History of intolerance to bupropion or dextromethorphan.
7. Unable or unlikely to comply with the study protocol or unsuitable for any other reason, including other conditions that might indicate that the subject is unsuitable for the study as judged by the investigator such as known history of poor medication compliance or significant instability in status of psychosocial issues.
8. Previously received treatment with any investigational drug (other than AXS-05) or device within 30 days of Visit 1.

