**Exclusion Criteria:**

A subject will be excluded from the study if the subject meets any of the following criteria:

- 1. History of seizure disorder; undergoing abrupt discontinuation of alcohol, benzodiazepines, barbiturates or antiepileptic drugs; or any other condition that increases the risk of seizure such as stroke, significant head injury, tumor or infection of the central nervous system, arteriovenous malformation, neuroleptic malignant syndrome/serotonin syndrome, or clinically significant, as deemed by the investigator, metabolic disorders (e.g., clinically significant hypoglycemia, hyponatremia, severe hepatic impairment, and hypoxia).
- 2. Is considered by the investigator, for any reason (including, but not limited to, the risks described as precautions, warnings, and contraindications in the current version of the Investigator's Brochure for AXS-05 tablets), to be an unsuitable candidate to receive AXS-05.
- 3. If the subject is currently receiving or plans to use drugs with known bupropion interactions (as listed in the Wellbutrin SR package insert), Principal Investigator is aware of any potential drug interaction and has deemed the subject acceptable to participate.
- 4. Any current or recent medical, psychiatric, or social condition that, in the investigator's opinion, is likely to interfere with the conduct of the study, confounds the interpretation of study results, or endangers the subject's well-being. This includes (but is not limited to) any clinically significant oncologic, hematologic, endocrine/metabolic, cardiovascular, respiratory, renal, hepatic, gastrointestinal, infectious or neurologic disease or has a chronic disease which is unstable or progressive.
- 5. History of allergy or hypersensitivity to bupropion, dextromethorphan, opiate drugs (e.g., codeine), or any other ingredient in the study medication.
- 6. History of intolerance to bupropion or dextromethorphan.
- 7. Unable or unlikely to comply with the study protocol or unsuitable for any other reason, including other conditions that might indicate that the subject is unsuitable for the study as judged by the investigator such as known history of poor medication compliance or significant instability in status of psychosocial issues.
- 8. Previously received treatment with any investigational drug (other than AXS-05) or device within 30 days of Visit 1.

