## **7.2. Study Entry Criteria**

### **7.2.1. Inclusion Criteria**

A subject will be eligible for participation if all of the following criteria are met:

1. Male or female outpatients, 18 to 65 years of age, inclusive. Subjects who participated in Study AXS-05-TRD-201 eligible regardless of age at entry into this study.
2. Completed Study AXS-05-TRD-201 OR currently meets the DSM-5 criteria for MDD without psychotic features.
3. Provides written informed consent to participate in the study, is able to understand the procedures and study requirements, and agrees to abide by the study restrictions and return for the required study assessments.
4. If female and of childbearing potential, has a negative urine pregnancy test result at Visit 1, is practicing at least two adequate methods of birth control (i.e., oral or parenteral contraceptives, intrauterine device, condoms, spermicides), and is not currently pregnant or breastfeeding nor plans to become pregnant during the course of the study.
  - a. Long-term abstinence is acceptable when it is in line with the subjects preferred and usual lifestyle.
  - b. Female subjects using a hormonal contraceptive or intrauterine device must have been doing so for at least 1 month before Screening and must follow that product's package insert instructions including additional protection at times when hormonal contraceptive doses might be missed.
  - c. Female subjects may be enrolled without a negative urine pregnancy test if they are surgically sterile or at least 2 years post-menopausal.
  - d. Male subjects and their female sexual partners should use an acceptable method of birth control (as noted above) during the study.

*Subjects who did not participate in Study AXS-05-TRD-201 must also meet the following criteria:*

5. [REDACTED]
6. Have been treated with at least 1 prior ADT in the current major depressive episode.
7. Male or female outpatients, 18 to 65 years of age, inclusive.

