## **8.13. Prohibited Therapies**

The following concomitant medications are not allowed during this study:

- Drugs with known bupropion interactions (as listed in the Wellbutrin SR package insert)
- Drugs containing dextromethorphan or bupropion (other than AXS-05)
- Monoamine oxidase inhibitors (MAOIs)
- Linezolid
- Intravenous methylene blue

Beyond the above listed items, there are no restrictions on concomitant medications during this study.

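### Exclusion criterion 3 reads as a condition for acceptance and is not aligned with the ban on the same drug class in Protocol Section 8.13

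*Protocol*

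**What the plan says.** Protocol Section 7.2.2 opens its list with "A subject will be excluded from the study if the subject meets any of the following criteria". Criterion 3 in that list begins "If the subject is currently receiving or plans to use drugs with known bupropion interactions (as listed in the Wellbutrin SR package insert" and closes with "Principal Investigator is aware of any potential drug interaction and has deemed the subject acceptable to participate". The synopsis repeats the criterion.

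Protocol Section 8.13 starts from "The following concomitant medications are not allowed during this study", and its first item is "Drugs with known bupropion interactions (as listed in the Wellbutrin SR package insert". Its last sentence is "Beyond the above listed items, there are no restrictions on concomitant medications during this study". It mentions neither investigator acceptance nor criterion 3, and criterion 3 does not mention Section 8.13.

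Three other provisions bear on the matter in general terms:

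- Section 7.2.1 sets the rule "A subject will be eligible for participation if all of the following criteria are met", and its criterion 3 requires that the subject "agrees to abide by the study restrictions and return for the required study assessments".
- Exclusion criterion 7 removes subjects who cannot, or probably will not, follow the protocol.
- Section 9 counts the stopping of prohibited therapy among the steps that need prior consent.

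None of the three names this drug class or refers to exclusion criterion 3.

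**The concern.** There are two faults. The first is that criterion 3 is inverted. Every other item in the list describes a subject who should not enter; this one describes a subject who has been found fit to enter.

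The second is that the permission criterion 3 seems to give does not match the ban in Section 8.13. One site could take criterion 3 as the specific rule for this class and enrol a subject who plans to use a listed drug. Another could apply Section 8.13 together with inclusion criterion 3 and exclusion criterion 7, and refuse the same subject. After entry, the same use could count as accepted at one site and as a deviation at another. Section 7.3 lets the sponsor request withdrawal for protocol violations, and under Section 7.4 withdrawn subjects are not replaced.

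The primary endpoint is the incidence of treatment-emergent adverse events. Which interacting drugs may be taken with study drug should therefore not depend on which section a site consults.

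**Working it through.** No arithmetic decides this point, so the check sets the texts side by side.

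| Question | Criterion 3 (Section 7.2.2 and synopsis) | Section 8.13 |
|---|---|---|
| Drug class | Known bupropion interactions | Known bupropion interactions |
| Source of the list | Wellbutrin SR package insert | Wellbutrin SR package insert |
| Use covered | Current and planned | Any use during the study |
| Outcome | Investigator aware and accepting | Not allowed |
| Exception | Not applicable | None stated |
| Reference to the other | None | None |

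1. **Literal reading.** Meeting an item excludes. Criterion 3 is met when a user of a listed drug has been accepted by the investigator. The accepted user is then excluded, which contradicts the criterion's own closing words. Items 1, 2 and 4 to 8 each state a disqualifying condition; item 3 is the only one that does not.

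2. **Apparent intent.** A user may enter if the investigator knows of the interaction and accepts the subject. This has to be tested separately for each kind of use.
   - *Current use.* Section 9 foresees that prohibited therapy may be stopped after consent. A current user who stops can satisfy both criterion 3 and Section 8.13.
   - *Planned or continued use.* For a subject entering the study, planned use is naturally use during the study, and so is use that continues after entry. Section 8.13 bans both. Stopping a current drug does not reconcile a plan to take one later.

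3. **Do the general clauses settle it?** All inclusion criteria must be met, and any one exclusion criterion is enough to exclude. Read with Section 8.13, inclusion criterion 3 and exclusion criterion 7 would bar a subject who intends to use a banned drug. That yields an answer, but it leaves criterion 3's apparent acceptance of planned users with nothing to apply to.

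4. **Is there another clause that permits the use?** Section 10.2.4 allows a subject to continue when treatment of an adverse event deviates from the protocol. That is a different situation, and the discretion belongs to the sponsor rather than to the investigator under criterion 3.

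5. **Can the use be seen afterwards?** Yes. Section 8.12 has medications recorded at each visit, and SAP Section 8.4 summarises them by ATC level 4. Protocol Section 12.4.1.2 has the sponsor classify major deviations before database lock. SAP Section 8.5 summarises major deviations but does not say whether investigator-accepted use of this class is one.

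6. **How many subjects?** The plan is for about 150 subjects at up to about 25 sites. Neither figure indicates how many would take a listed drug, and the package insert that defines the class is not part of the documents. No count can be given.

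**The case against.** The strongest reply is that the protocol already bars this use. Section 8.13 is a flat ban in a section of its own, and it applies whether or not the eligibility list cites it. Inclusion criterion 3 and exclusion criterion 7 reinforce it at entry, and Section 9 provides for current users to stop. On this view criterion 3 is a clumsily worded check that the investigator knows of the interaction. No site would apply the literal reading, because it defeats itself. Divergence between sites is conjecture, the drug use remains visible in the data, and no analysis depends on it, so the point is editorial.

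Much of this stands. Current users who stop can be reconciled. The literal reading shows a drafting error rather than a rival rule that sites are likely to follow. The documents do not show that sites will differ. A missing cross-reference alone would be minor.

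Two things remain. Planned use, which criterion 3 names expressly, cannot be reconciled with Section 8.13. The general clauses close the gap only by leaving that part of a specific eligibility criterion without effect. A criterion that has to be disregarded to be consistent with the rest of the protocol needs correcting, even if most sites would guess the intent.

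**Conclusion.** The concern holds. Criterion 3 is wrong as written in an operative eligibility list and in the synopsis, and its apparent permission for planned use is not aligned with Section 8.13. Confidence is high for the wording and for the missing alignment, since both can be read directly from the text. It does not extend to how sites would act.

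The conclusion assumes that planned use means use during the study. The reach is narrow: subjects who plan to take a listed drug, or who continue one after entry, in number unknown. The consequence is confined to who is eligible and whether the same use is treated as accepted or as a deviation. No estimate, sample size or analysis population changes. This should be fixed because it is an eligibility rule that bears on safety and is cheap to correct; it does not threaten the study's analyses.

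**What to change.** Reconcile the synopsis exclusion list, Section 7.2.2 and Section 8.13 so that they state one rule for current, continued and planned use of this class. Reword criterion 3 so that meeting it excludes, and cross-reference Section 8.13. Check the result against inclusion criterion 3 and exclusion criterion 7. The choice of clinical rule belongs to the sponsor's medical team; the statistical request is only that the passages give one answer.

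The cost is a wording amendment and a memo to sites. Under Section 13.6 the amendment needs the sponsor's written approval, the investigator's signature, IRB/IEC approval before use at a site, and filing with the regulatory agencies. No new procedure and no SAP change is needed.

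The SAP leaves the enrolment status unclear: Section 4.1 speaks of planned enrolment in the past tense, while Section 7.2 says the study is enrolling. If enrolment has closed, rewording the entry criterion changes little. A note made before database lock, saying how investigator-accepted use of this class is classified as a deviation, would then cover most of what remains.

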### **7.3. Premature Subject Withdrawal**

All subjects will be advised that they are free to withdraw from participation in this study at any time, for any reason, and without prejudice. The investigator should make every reasonable attempt to keep subjects in the study; however, subjects must be withdrawn from the study if they withdraw consent to participate. The investigator or designee must attempt to contact subjects who fail to attend scheduled visits by telephone or other means to evaluate the possibility of an AE being the cause of withdrawal. Should this be the cause, the AE must be documented, reported, and followed as described in [Section 10.2](#).

Axsome reserves the right to request the withdrawal of a subject because of protocol violations or other reasons.

The investigator also has the right to withdraw subjects from the study or discontinue study drug treatment at any time for lack of therapeutic effect that is intolerable or otherwise unacceptable to the subject, for intolerable or unacceptable AEs, intercurrent illness, noncompliance with study procedures, administrative reasons, or in the investigator's opinion, to protect the subject's best interest.

If a subject is withdrawn or discontinues treatment before completing the study, the reason and the date of discontinuation will be recorded on the appropriate electronic case report form (eCRF). If the subject received study drug prior to discontinuation, all attempts should be made to complete the end of study evaluations.

#### **7.4. Subject Replacement Criteria**

Subjects who are withdrawn will not be replaced. If a substantial number of subjects are withdrawn from the study, then Axsome will evaluate the need for developing replacement criteria.

### **8. TREATMENTS**

#### **8.1. Identification of Investigational Product**

The following study medications will be provided:

- **AXS-05:** a tablet consisting of 45 mg dextromethorphan hydrobromide monohydrate and 105 mg bupropion hydrochloride sustained release in the form of a bilayer tablet for oral administration

#### **8.2. Labeling and Packaging**

##### **8.2.1. Labeling**

The bottles of the study drug will have a label that meets the applicable regulatory requirements and may include the following: subject identifier, dosage strength, lot number, package number, protocol number, specified number of tablets, caution statement, storage, sponsor/manufacturer identification, and dosing instructions.

##### **8.2.2. Packaging**

The study drug will be packaged in bottles, which will include 30 tablets.

#### **8.3. Study Medication Administration**

Study drug will be dispensed and/or re-dispensed to eligible subjects at each visit.

#### **8.4. Dispensing and Storage**

The study drug is to be used exclusively in this clinical study according to the instructions of this protocol. The investigator or designee is responsible for dispensing the study drug according to the dosage scheme and for ensuring its proper storage.

The investigator or designee must confirm the receipt of the study drug. A copy of this receipt must be kept by the investigator or designee and another copy will be stored at Axsome and/or its designee. The study drug will be dispensed and/or re-dispensed to the subject at each visit.

Once study drug has been received on site it must be stored at 25°C (77°F) and in a dry place in a securely locked area that is not generally accessible. Excursions between 15° and 30°C (59° and 86°F) are permitted. The storage area will be accessible only to those persons authorized by the investigator.

#### **8.5. Method of Assigning Subjects to Treatment**

This is an open-label study; all subjects will receive AXS-05.

#### **8.6. Blinding and Unblinding Treatment Assignment**

Not applicable as this is an open-label study.

#### **8.7. Selection of Doses in the Study**

The dose of AXS-05 (45 mg DM HBr, 105 mg bupropion HCl) [REDACTED]  
[REDACTED] was selected based on the results of pharmacokinetic Phase 1 trials of AXS-05. The selected dose resulted in the targeted plasma concentrations of the components of AXS-05.

#### **8.8. Selection of Timing of Dose for Each Subject**

A significant food effect has not been reported for AXS-05; therefore, study drug may be taken with or without food.

The timing of the dose (twice daily) was selected based on the results of the previously completed studies in subjects with depression.

#### **8.9. Dose Adjustment Criteria**

Dose adjustment is not allowed during this study.

#### **8.10. Drug Accountability**

The investigator, or designee, must maintain adequate records showing the receipt, dosing, or other disposition of the study drug provided, including the date, quantity, batch or code number, and identification of subjects (subject number) who received it. The investigator will not supply the study drug to any person except those named as sub-investigators on the Form FDA 1572, designated study personnel, and subjects in this study. The investigator will not dispense the study drug from any study sites other than those listed on the Form FDA 1572. The study drug may not be relabeled or reassigned for use by other subjects. If any of the study drug is not dispensed; is lost, stolen, spilled, unusable; or is received in a damaged container, this information must be documented and reported to Axsome Therapeutics and appropriate regulatory agencies, as required.

Upon completion of the study, the study drug (unused and empty packaging, e.g., study drug bottles) must be left in the original packaging and returned to Axsome or its designee for destruction.

#### **8.11. Treatment Compliance**

Study drug compliance will be closely monitored by counting the number of tablets dispensed and returned.

Subjects will be instructed to bring any unused study drug and empty containers to the clinic at each visit or at the time of early study discontinuation. Before new study drug is dispensed at each visit, every effort will be made to collect the unused study drug to confirm compliance.

Investigators will perform drug accountability of study drug at each visit to determine a subject's usage. Study drug compliance will be assessed at the 80-120% level.

## **8.12. Prior and Concomitant Therapies**

Medication history during the previous 1 year (5 years in the case of psychiatric drug history) will be recorded in the eCRF. Thereafter, any changes in concomitant medications or new medications added will be recorded in the case report form (CRF).

At each visit, subjects will be queried as to whether or not they have taken any concomitant medications and, if so, the Investigator will record the medications taken and the reasons for their use. All concomitant medications and treatments used (including over-the-counter medications and herbal supplements) will be recorded in the source document and on the appropriate CRF.

## **8.13. Prohibited Therapies**

The following concomitant medications are not allowed during this study:

- Drugs with known bupropion interactions (as listed in the Wellbutrin SR package insert)
- Drugs containing dextromethorphan or bupropion (other than AXS-05)
- Monoamine oxidase inhibitors (MAOIs)
- Linezolid
- Intravenous methylene blue

Beyond the above listed items, there are no restrictions on concomitant medications during this study.

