9. EFFICACY

This is a long-term and open-label safety study, and safety evaluation is the primary objective. The efficacy assessments are secondary and will be analyzed appropriately. Efficacy analyses will be performed on the mITT population.

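### Later-visit MADRS response and remission rates can mix AXS-05 outcomes with those of antidepressants started during the study, and no legible planned summary shows by how much

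*Protocol*

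**What the plan says.** **Permitted medication.** Protocol 8.13 bars drugs with known bupropion interactions (by reference to a package insert), other products containing dextromethorphan or bupropion, MAOIs, linezolid and intravenous methylene blue. It then says: "Beyond the above listed items, there are no restrictions on concomitant medications during this study". Antidepressants as a class are not on the list. Treatment lasts up to 15 months (Protocol 6.1).

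**Data collected.** Under Protocol 8.12, "any changes in concomitant medications or new medications added will be recorded", and at each visit the reasons for use are recorded as well. SAP 8.4 codes medications to ATC Level 4. SAP 8.4 and Appendix 1 use start and stop dates, but only to sort medications into prior and concomitant tables for the Safety population.

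**Efficacy analysis.** SAP 9 states: "Efficacy analyses will be performed on the mITT population". SAP 7.4.2 defines that population by enrolment, one dose and one post-baseline efficacy assessment, without reference to other treatment. SAP 9.1 summarises MADRS change, response (at least 50% improvement) and remission (total score of 10 or less) over time, by group and overall. Week 6 is the primary timepoint, and Weeks 1 and 2 are key secondary. After Week 6 the MADRS is scheduled at Months 2, 3, 6, 9, 12 and 15.

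**The concern.** The secondary objective (SAP 3.2) is the long-term efficacy outcome of AXS-05 in TRD. A subject who starts another antidepressant at, say, Month 4 and is in remission at Month 6 is counted as a Month 6 remitter in the same way as a subject on AXS-05 alone. There is no concurrent control arm with the same freedom to add treatment, so nothing in the design offsets this.

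Subjects doing poorly are plausibly the ones most likely to have treatment added, and the opportunity grows with time. The later visits, which the long-term objective is about, are therefore the most exposed. If additions differ between Rollover AXS-05, Rollover Placebo and Direct Entry subjects, the side-by-side columns are affected too, as are the between-treatment comparisons that SAP 9.1 leaves open.

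The medication table and the efficacy tables are planned separately. A reader of both could see which drug classes were used, but not how many remitters at a given visit had already started one.

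**Working it through.** **1. Text check.** The plan states no figure on this point, so there is nothing to reproduce. The sample size of about 150 has no stated effect size, SD, rate or dropout behind it. The question is whether any provision links added antidepressants to efficacy:

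- Protocol 8.13: restriction by listed item, not by antidepressant effect.
- SAP 7.4.2: no exclusion from mITT for other treatment.
- SAP 8.4 and Appendix 1: dates used for classification only.
- SAP 9 and 9.1: no censoring rule, subgroup, flag or sensitivity analysis for a newly started antidepressant in the legible text.

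No such link is found.

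**2. Illustration of size (assumed inputs).**

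- *p*, the observed remission rate at a later visit: not given for this study. I use 40%, rounded from the 39.5% at Week 6 in the AXS-05 arm of the Phase 3 MDD trial (Protocol 4.2.1), with a range of 30% to 60%. That trial was in MDD, not TRD, and lasted 6 weeks.
- *f*, the share of remitters who had started another antidepressant: not given; assumed 5% to 30%.
- *n* = 150, the planned enrolment. Numbers at later visits cannot exceed those enrolled, so at a given *p* the half-widths below are minimum values.

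Counting those remitters as non-remitters gives a rate of *p*(1 − *f*), a shift of *pf*. For scale, the 95% half-width is 1.96 × √(*p*(1 − *p*)/150).

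Worked for *p* = 40%: 0.40 × 150 = 60 remitters. With *f* = 5%, 3 are reclassified and 57/150 = 38.0%. With *f* = 30%, 18 are reclassified and 42/150 = 28.0%. The half-width is 1.96 × √(0.40 × 0.60/150) = 7.8 points.

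| | *p* = 30% | *p* = 40% | *p* = 50% | *p* = 60% |
|---|---|---|---|---|
| Rate, *f* = 5% | 28.5% | 38.0% | 47.5% | 57.0% |
| Rate, *f* = 10% | 27.0% | 36.0% | 45.0% | 54.0% |
| Rate, *f* = 20% | 24.0% | 32.0% | 40.0% | 48.0% |
| Rate, *f* = 30% | 21.0% | 28.0% | 35.0% | 42.0% |
| 95% half-width (points) | 7.3 | 7.8 | 8.0 | 7.8 |
| *f* at which shift = half-width | 24.4% | 19.6% | 16.0% | 13.1% |

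At *p* = 40% the shift is 2 to 12 points and passes the sampling half-width once about one remitter in five has added treatment.

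**3. Side check on the interaction rule.** Section 8.13 lists drugs with known bupropion interactions as not allowed. Exclusion 3 (Protocol 7.2.2) addresses subjects who are receiving or plan to use the same drugs, and speaks of the case where the "Principal Investigator is aware of any potential drug interaction and has deemed the subject acceptable to participate". One provision prohibits and the other turns on the investigator's acceptance. The range of antidepressants available during the study depends partly on which applies.

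**The case against.** The strongest reply is that the planned summary is legitimate as it stands. In an open-label safety study with efficacy secondary, outcomes regardless of added medication are a treatment-policy summary, and the SAP nowhere says that they are due to AXS-05 alone. That stands, and it is why the planned table should remain the main one. It does not remove the value of showing how much added treatment lies behind the later rates.

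Three other points limit the concern:

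- **Scope.** Week 6 is the primary efficacy timepoint, and there is less time for additions before it. The concern is mainly with later, descriptive visits.
- **Other information.** SAP 7.1 commits to listings of all CRF data, so medication records and MADRS scores will be available for each subject. SAP 8.4 tabulates concomitant medications by group. These would let someone reconstruct the answer by hand, but neither is a summary by visit. Protocol 7.3 also allows withdrawal for lack of effect, so added treatment is not the only course for a subject doing poorly.
- **Redaction.** Seven items in SAP 9.1 are blacked out, so the absence of a rule can be confirmed only for legible text.

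A reader might infer that any antidepressant may be added freely. The documents do not support that: MAOIs, other bupropion products and listed interacting drugs are barred under 8.13, and the list of interacting drugs cannot be seen.

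**Conclusion.** The point holds as a cheap improvement. Antidepressants outside the 8.13 list may be started, the start dates, ATC classes and reasons for use are collected or coded, and no legible efficacy summary uses them. Later-visit response and remission therefore cannot be read as outcomes of AXS-05 alone.

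The size is unknown. The fall from 40% to between 38% and 28% rests wholly on the assumed 5% to 30% share of remitters and on a remission rate borrowed from a different population.

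A reader might take the 2 to 12 points as upward bias. They are not an estimate of bias. They show how many remissions would be reclassified, and would equal bias only if the target were remission without added antidepressants and none of those subjects would have remitted otherwise. The documents support neither condition.

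**What to change.** Keep the mITT summary in SAP 9.1 as the main one. Add one supplementary table by visit and group (Rollover AXS-05, Rollover Placebo, Direct Entry, Overall), with the same denominators as the planned table, giving:

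- (a) the number and percentage of subjects who have newly started another antidepressant since the first dose in this study, identified by ATC class together with the recorded reason for use, since class alone does not show indication;
- (b) MADRS response and remission with every visit on or after that start counted as non-response and non-remission.

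Three details belong in the text:

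- Do not drop change scores after an addition. That would remove the subjects likely to do worst and could raise the mean change.
- Include dose increases only if the CRF captures dose. Protocol 8.12 records changes but does not say that dose is among them.
- Flag subjects whose start date was imputed. Appendix 1 sets a start date with a missing month to January 1, which can place the start months early or even before the first dose. A completely missing start date is classified but given no date, so flag these too.

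The cost is one extra table from data already collected, and late response and remission rates that may look less favourable. No change to permitted medication is proposed. Separately, Exclusion 3 and Section 8.13 must be reconciled on interacting drugs; which is right is not for this review to say.
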